3.2. Subject Randomization

At Visit 2/Treatment Day, subjects will be randomized (1:1:1 ratio) to treatment with either 20U onabotulinumtoxinA, 20U prabotulinumtoxinA-xvfs, or 40U prabotulinumtoxinA-xvfs.

Subjects will be randomized using a blocked randomization scheme that will be stratified by the following factors:

• Baseline GLS: moderate vs. severe

• Age group: <65 vs. >65 within each stratum

• Gender: female vs male

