7. STATISTICAL METHODS

7.1. Primary Effectiveness Endpoint

The primary effectiveness endpoint will be duration of effect (regardless of responder status), defined as the number of days from Treatment Day (Baseline) to the day that GLS severity (Investigator assessment) at maximum frown returns to the Baseline value. Although the trial is not powered for inferential analysis, this will be the most influential outcome in the overall assessment of the effectiveness of prabotulinumtoxinA 40 Units, compared to prabotulinumtoxinA 20 Units, in treating moderate to severe glabellar lines. Analysis will be performed using the modified Intent-To-Treat (mITT) population and regardless of responder status.

Duration of effect will be described by Kaplan-Meier curves and the respective median times with associated 2-sided 95% confidence interval (CI) for each treatment group. Statistical analyses of treatment group differences will be done using Cox proportional hazards regression with time to return to Baseline as the dependent variable, treatment group as the independent variable, and age, gender, and Baseline GLS score (Investigator assessment) at maximum frown as covariates.

Statistical significance will be established at the 0.025 level with one-sided hypothesis testing.

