7.3. Exploratory Effectiveness Endpoints

Exploratory effectiveness endpoints will be evaluated for signals of effectiveness to explore whether any should be elevated in importance for subsequent trials. These endpoints will be assessed using either logistic regression (for binary endpoints) or survival analysis-type methods as described above. Comparisons will be made between all treatment groups. Chi-square tests of association or Fisher's exact tests will be used to compare treatment group differences in proportion of subjects returning to Baseline at each time point in the study. Exploratory endpoints will be:

Version 1.1 31-May-2023 Confidential Page 18/58

- 1. Duration of effect for GLS responders, defined as the number of days from Treatment Day (Baseline) to the day that GLS severity at maximum frown returns to the Baseline value. Analyses will be conducted for Investigator and subject assessments of GLS. Various responder definitions will be tested (1-Point, 2-Point and 3-Point responders at any time during the study; GLS Score of 0 or 1 at any time during the study; 1-Point responders at Day 30).
- 2. Time to loss of GLS responder status, with responder being defined as a GLS score of 0 or 1 at any point during the study. Analyses will be conducted for Investigator and subject assessments of GLS.
- 3. GLS responder rates (Investigator assessments) at each study visit. Various responder definitions will be tested (1-Point, 2-Point and 3-Point responders; GLS Score of 0 or 1; GLS Score 0 or 1 & ≥2-Point improvement; GLS Score 0 or 1 & ≥2-Point improvement & Investigator GLS = subject GLS).
- 4. GLS responder rates (Subject assessments) at each study visit. Various responder definitions will be tested (1-Point, 2-Point and 3-Point responders; GLS Score of 0 or 1).
- 5. GAIS response (score of 2 or 1) as assessed by Investigator and subject at each visit.
- 6. SSS response (score of 2 or 1) as assessed by subjects at each visit.
- 7. Onset of effect as assessed by subjects through the 7-Day Subject Diary.

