14.3 Efficacy Response Data

14.3.1 Primary Effectiveness Endpoint - Duration of Effect

Table 14.3.1.1 Duration of Effect (Investigator; Regardless of Responder Status; PraB 40 vs PraB 20)

GLS (Investigator) Duration of Effect	PraB 40	PraB 20
(Return to Baseline GLS score)	$(\mathbf{n} = \mathbf{x}\mathbf{x})$	$(\mathbf{n} = \mathbf{x}\mathbf{x})$
Subject Status, n (%)		
Returned to BL (event)	xx (xx%)	xx (xx%)
Censored	xx (xx%)	xx (xx%)
Kaplan-Meier Estimates for Return to BL		
1 st Quartile, (95% CI)	x.x(x.x, x.x)	x.x(x.x, x.x)
Median, (95% CI)	x.x(x.x, x.x)	x.x(x.x, x.x)
3 rd Quartile, (95% CI)	x.x(x.x, x.x)	x.x(x.x, x.x)
Adjusted Hazard Ratio (95% CI)	x.xx (x.:	xx, x.xx)
Stratified Log-Rank p-value	p <x.< td="">xxxx	</x.<>	xxxx
Unadjusted Hazard Ratio (95% CI)	zard Ratio (95% CI) x.xx (x.xx, x.xx)	
Unstratified Log-Rank p-value	p <x.xxxx< td=""></x.xxxx<>	

Data for all subjects regardless of Responder status

Duration of effect in days, calculated from Visit 2 (Treatment Day) to when subject returns to Baseline GLS score Responder = At least 1-Point improvement in GLS (max frown)

Version 1.1 31-May-2023

Confidential Page 29/58

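### Return-to-Baseline proportions are tested without stratifying by Baseline GLS, and the covariates of the responder-rate models are not named: exploratory power may be lost

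*SAP*

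**What the plan says.** - **Randomisation.** SAP 3.2 and Protocol 6.2 describe blocked randomisation with three stratification factors. The first is "Baseline GLS: moderate vs. severe"; the others are age group and gender.
- **Primary analysis.** SAP 7.1 fits a Cox model with "age, gender, and Baseline GLS score (Investigator assessment) at maximum frown as covariates". The duration shells in Appendix A print adjusted and unadjusted hazard ratios, and beside the unstratified log-rank result a "Stratified Log-Rank p-value".
- **Return to Baseline by visit.** SAP 7.3 and Protocol 12.4: "Chi-square tests of association or Fisher's exact tests will be used to compare treatment group differences in proportion of subjects returning to Baseline". No stratified version is mentioned.
- **Other exploratory endpoints.** SAP 7.3: "These endpoints will be assessed using either logistic regression (for binary endpoints) or survival analysis-type methods as described above". No covariates are listed for the logistic models.
- **Responder shells (14.3.3.3.1 to 14.3.3.5.1).** Each prints a p-value beside the percentages with no test named. In separate rows it prints an odds ratio with its own interval and p-value, labelled neither adjusted nor unadjusted.

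**The concern.** Stratifying the randomisation makes the arms alike in Baseline grade. If grade predicts the outcome, the true sampling error of the difference between arms becomes smaller. A test that ignores grade still uses the larger error, so its p-values tend to be too large. The plan recognises this for the duration endpoints and departs from it for proportions.

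At stake is the use made of these results. SAP 7.3 says: "Exploratory effectiveness endpoints will be evaluated for signals of effectiveness to explore whether any should be elevated in importance for subsequent trials". With 50 subjects per arm, the error to worry about is missing a dose signal.

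**Working it through.** **The plan's own figures.** The documents state no power or effect size for any per-visit proportion. The only stated power, 80% in SAP 7.6, concerns the primary time-to-event comparison. With its inputs and 12 months' follow-up, expected events are 50 × Σ λ/(λ+γ) × (1 − e^(−12(λ+γ))), with λ = ln2/4 and 0.47 × ln2/4 and γ = −ln(0.9)/12. That gives about 72 events. Power is Φ(½√72 × ln(1/0.47) − 1.96) = 0.893 by the Schoenfeld formula. The stated 80% is therefore not reproduced, but it errs on the cautious side and does not bear on this point.

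**Inputs.** From the documents: 50 per arm, reference median 4 months and hazard ratio 0.47 (SAP 7.6); stratification by grade (SAP 3.2); GLS scored 0 to 3 (SAP 5.1.1), with entry at 2 or 3 (Protocol 5.1). Assumed: half of subjects severe, exact balance of arms within grade, two-sided 0.05, a within-grade odds ratio of 3.2 (about 79% power at a 50% control rate), and the response rates by grade.

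**Step 1: why the unstratified test is conservative.** With two equal grades, p̄(1−p̄) = mean of p(1−p) within grade + variance of p between grades. The unstratified test uses the left side. Under stratified randomisation only the first term on the right is sampling error. The ratio of true to assumed standard error is r = √(within/total), and actual type I error is roughly 2 × (1 − Φ(1.96/r)).

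| Control rates by grade | Within / total | r | Approx. type I error |
|---|---|---|---|
| 50% / 50% | 0.25 / 0.25 | 1.00 | 0.050 |
| 60% / 40% | 0.24 / 0.25 | 0.98 | 0.045 |
| 70% / 30% | 0.21 / 0.25 | 0.92 | 0.032 |
| 80% / 20% | 0.16 / 0.25 | 0.80 | 0.014 |

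**Step 2: simulated power and type I error (20,000 trials per case).**

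| Gap between grades | Power: chi-square → Cochran-Mantel-Haenszel (CMH) | Type I error: chi-square / CMH |
|---|---|---|
| 0 points | 0.789 → 0.790 | 0.058 / 0.058 |
| 20 points | 0.766 → 0.774 | 0.051 / 0.051 |
| 40 points | 0.681 → 0.732 | 0.040 / 0.052 |
| 60 points | 0.486 → 0.641 | 0.018 / 0.049 |

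The losses are about 0, 1, 5 and 16 percentage points. The 0.058 with no gap is the same for both tests; it comes from the discreteness of the counts, not from ignoring grade. With 30% to 70% severe, the loss at the 60-point gap is 10 to 16 points. Fisher's test is conservative in its own right: 0.036 with no gap.

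**Step 3: return to Baseline at Day 120, on the plan's inputs.** A 4-month median gives 50% returned in the reference arm, and 1 − 0.5^0.47 = 28% on 40 Units. Suppose one grade has k times the hazard of the other and the reference average stays at 50%. If x is the share not yet returned in the slower grade, then x + x^k = 1. The hazard ratio of 0.47 is applied within each grade.

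| k | Reference rates by grade | Gap | Power: unstratified → stratified |
|---|---|---|---|
| 2 | 38% / 62% | 24 points | 61.8% → 62.7% |
| 3 | 32% / 68% | 36 points | 59.2% → 62.3% |
| 4 | 28% / 72% | 45 points | 55.9% → 62.0% |

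The gains are about 1, 3 and 6 points.

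**Step 4: responder definitions and Baseline grade.**
- ≥2-point: needs a score of 0 from moderate, but 0 or 1 from severe.
- Score of 0 or 1: needs one point from moderate, but two from severe.
- ≥3-point: impossible from moderate; needs a score of 0 from severe.
- ≥1-point: the same one-point change from either grade.
- GAIS and SSS: not defined by Baseline GLS.

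Logistic regression without versus with Baseline GLS repeats the pattern. Power is 0.672 versus 0.724 at the 40-point gap and 0.466 versus 0.618 at the 60-point gap. The median odds ratio is 2.70 and 2.15 without GLS, against 3.27 with it.

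**The case against.** - **Responder rates are not shown to be unadjusted.** A reader might infer that the responder comparisons use plain chi-square tests or unadjusted odds ratios. The documents do not support that. The chi-square/Fisher sentence covers only return to Baseline. Responder rates get logistic regression, and the reference back to methods already described could carry over the SAP 7.1 covariates. This part is a gap in specification.
- **A loss of power is not established.** It is tempting to say flatly that p-values are too large. That holds only as far as Baseline GLS is prognostic, and no rates by grade are given. With no prognostic effect, the stratified p-value was the smaller one in only about 15% of simulated trials.
- **The crude odds ratio is not biased.** Its distance from the adjusted one reflects non-collapsibility. It is a valid marginal measure, but it should be labelled.
- **Balance fades over time.** Under Protocol 10.2.5 subjects may exit from Day 90 once back at Baseline, and SAP 7.7 analyses non-duration exploratory data as observed. The simulated figures assume full balance and do not transfer directly to late visits.
- **The consequence is limited.** The endpoints are exploratory, the trial is described as not powered for inference, and the primary comparison already adjusts for Baseline GLS.

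All five stand. They limit the point's size without removing it: the return-to-Baseline test is unstratified as written, and the responder shells leave the method open.

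**Conclusion.** The concern holds in a conditional form and is minor. The per-visit return-to-Baseline tests ignore a factor used in randomisation and in the primary model. The cost is negligible if rates differ between grades by no more than about 20 points, about 5 points of power at a 40-point gap and about 16 at 60. These sizes rest on the assumed rates, the within-grade odds ratio of 3.2, half of subjects severe and balanced arms. Any error is in the conservative direction.

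For responder rates the finding is an unnamed covariate set, an unlabelled odds ratio and an unnamed test. It matters most for the ≥2-point and 0-or-1 definitions, where the change required depends on Baseline grade.

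**What to change.** 1. In SAP 7.3, replace the chi-square/Fisher comparison of return to Baseline with a Cochran-Mantel-Haenszel test stratified by Baseline GLS, exact when counts are small. Appendix A has no shell for this per-visit comparison, so say where it will be reported.
2. Name the same test as the source of the p-value beside the percentages in shells 14.3.3.3.1 to 14.3.3.5.1.
3. State that the logistic models include age, gender and Baseline GLS as in SAP 7.1, and label the odds ratio as adjusted.
4. Make an exception for the ≥3-point response. No moderate subject can reach it, so ordinary logistic regression cannot estimate the GLS coefficient. Use the stratified exact or Cochran-Mantel-Haenszel test there.
5. Keep the crude percentages as descriptive.

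The cost is SAP wording, shell labels and a few lines of SAS. All the variables are already collected. Where Baseline GLS has no prognostic effect, power is essentially unchanged (0.789 against 0.790).

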#### **Phase III European Clinical Trial for Glabellar Lines**

The EVB-003 study was the third Phase III safety and efficacy study in the prabotulinumtoxinA clinical development program and was conducted in Europe and Canada (REF 3). 540 subjects with moderate to severe glabellar lines, or a GLS score of 2 or 3, as assessed by the investigator at maximum frown, were eligible to be enrolled provided that subjects also felt their glabellar lines had an important psychological impact, such as on their mood, anxiety, or depressive symptoms. On Day 0, eligible subjects were randomly assigned in a 5:5:1 ratio to receive a single treatment of 20 units of prabotulinumtoxinA, 20 units of onabotulinumtoxinA or placebo.

The primary efficacy endpoint was defined as the proportion of subjects classified as responders on Day 30. A responder was a subject with a GLS score of 0 or 1, as assessed by the investigator at maximum frown. The primary analysis of the primary efficacy endpoint in the EVB-003 study showed prabotulinumtoxinA's superiority over placebo, and established prabotulinumtoxinA's non-inferiority to BOTOX. The percentages of responders for the primary efficacy endpoint were:

- 4.2% in the placebo group, 95% CI (0.0, 9.8);
- 82.8% in the onabotulinumtoxinA group, 95% CI (78.1, 87.5); and
- 87.2% in the prabotulinumtoxinA group, 95% CI (83.0, 91.5).

The absolute differences between the treatment groups were:

- 83.1% between prabotulinumtoxinA and placebo groups, 95% CI (70.3, 89.4), (p<0.001), indicating prabotulinumtoxinA was superior to placebo; and
- 4.4% between prabotulinumtoxinA and onabotulinumtoxinA groups, 95% CI (-1.9, 10.8), with non-inferiority of prabotulinumtoxinA versus onabotulinumtoxinA concluded based on the lower bound of the 95% CI for the absolute difference exceeding -10.0%.

As presented in the table below, within each group, 32.7% of placebo subjects, 41.9% of onabotulinumtoxinA subjects and 37.6% of prabotulinumtoxinA subjects experienced AEs. One placebo subject (1/49, 2.0%), one onabotulinumtoxinA subject (1/246, 0.4%) and three prabotulinumtoxinA subjects (3/245, 1.2%) experienced a total of 11 SAEs and none were assessed as study drug related. The eyelid ptosis rates were 1.6% in the prabotulinumtoxinA arm and 0% in the onabotulinumtoxinA arm and the eyebrow ptosis rates were 0% in the prabotulinumtoxinA arm and 0.4% in the onabotulinumtoxinA arm.

evolus™ evolus-cl	IN201 Version 2.0 23-Nov-2022	Confidential Page 19/68

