#### 12.4 Exploratory Effectiveness Endpoints

Exploratory effectiveness endpoints will be evaluated for signals of effectiveness to explore whether any should be elevated in importance for subsequent trials. These endpoints will be assessed using either logistic regression (for binary endpoints) or survival analysis-type methods as described above. Comparisons will be made between all treatment groups. Chi-square tests of association or Fisher's exact tests will be used to compare treatment group differences in proportion of subjects returning to Baseline at each time point in the study. Exploratory endpoints will be:

- 1. GLS score of 0 or 1 (maximum frown) as assessed by Investigator and subject at each visit.
- 2. GAIS response (score of 2 or 1) as assessed by Investigator and subject at each visit.
- 3. SSS response (score of 2 or 1) as assessed by subjects at each visit.
- 4. 1-point or greater, 2-point or greater, and 3-point or greater improvement on the GLS (maximum frown) as assessed by Investigator at each visit.
- 5. 1-point or greater, 2-point or greater, and 3-point or greater improvement on the GLS (maximum frown) as assessed by subject at each visit.
- 6. Duration of effect in responders with a 1-point or greater, 2-point or greater, and 3-point or greater improvement on the GLS (maximum frown) as assessed by Investigator at each visit.
- 7. Duration of effect in responders with a 1-point or greater, 2-point or greater, and 3-point or greater improvement on the GLS (maximum frown) as assessed subject at each visit.
- Buration of effect in GLS responders (responder = ≥1-point improvement on GLS at Day 30) as assessed by Investigator.
- Duration of effect in GLS responders (responder = ≥1-point improvement on GLS at Day 30) as assessed by subject.
- 10. Onset of effect as assessed by subjects through the 7-Day Subject Diary.

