7.6. Sample Size Considerations

This study is not powered for inferential analyses. Approximately 150 subjects will be randomized to the study, 50 subjects in each of the three treatment arms; 20U onabotulinumtoxinA, 20U prabotulinumtoxinA and 40U prabotulinumtoxinA. Assuming 50 subjects per treatment group, exponential distributions for failure and censoring times, a median duration of effect of 4 months in the reference group, and an annual censoring rate of 10%, the study will have 80% power to detect a hazard ratio of 0.47 based on a one-sided hypothesis test of the primary effectiveness endpoint with alpha = 0.025. As such, it is the opinion of the study Sponsor that 50 subjects per group (total sample size n=150) will be sufficient to address the objectives of this study.

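### GLS, GAIS and SSS are compared between arms at each visit only as yes/no responder cuts; adding one Baseline-adjusted ordinal comparison per scale would give a single, error-controlled and usually more powerful test from the same data.

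*SAP*

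**What the plan says.** SAP 7.3 lists the per-visit comparisons in items 3 to 6. Item 3 begins "GLS responder rates (Investigator assessments) at each study visit. Various responder definitions will be tested (1-Point, 2-Point and 3-Point responders" and adds GLS 0 or 1 and two combined definitions, six cuts in all. Item 4 applies four of them to the subject's GLS. Item 5 is "GAIS response (score of 2 or 1) as assessed by Investigator and subject at each visit", and item 6 treats SSS the same way, as does Protocol 12.4: "SSS response (score of 2 or 1) as assessed by subjects at each visit".

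On method, SAP 7.3 says "These endpoints will be assessed using either logistic regression (for binary endpoints) or survival analysis-type methods as described above". It names no covariates for the logistic models. Tables 14.3.3.3.1 to 14.3.3.5.1 have rows only for these cuts: a percentage per arm, then an odds ratio and p-value per pair of arms. The chi-square or Fisher comparison of return to Baseline at each time point is also yes/no. SAP 7.7 promises counts per category, which are descriptive. I found no ordinal, rank or mean-score comparison of these scales in either document.

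The scales are ordered: GLS has four grades, GAIS and SSS five each (SAP 5.1.1 to 5.1.3).

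**The concern.** SAP 7.3 gives these endpoints one job: to find signals that may deserve a higher rank in later trials. With 50 per arm, collapsing an ordered score usually costs power, and several of these cuts fit the trial poorly.

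- **Ceiling.** The Day 30 rate of GLS 0 or 1 in EVB-003 (Protocol 1.1) was "87.2% in the prabotulinumtoxinA group, 95% CI (83.0, 91.5", at 20U. That leaves little room for 40U to do better.
- **Impossible cut.** Entry requires Baseline GLS 2 or 3, so a moderate subject can never improve by 3 points.
- **Duplicate cut.** From Baseline 2 or 3, any improvement of 2 points already gives a score of 0 or 1. The combined definition that adds only this condition repeats the 2-point row.
- **Merged top grades.** The GAIS and SSS cuts pool the two best grades, where a higher dose might differ from 20U.

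Each visit and arm pair therefore carries 6 + 4 + 2 + 1 = 13 tests (Investigator GLS, subject GLS, two GAIS raters, SSS). None is ranked above another, and none uses the whole scale.

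**Working it through.** **The plan's own figure.** The documents give no power for the per-visit comparisons. Their one power statement, "the study will have 80% power to detect a hazard ratio of 0.47", concerns the primary endpoint. With its inputs and 12 months of follow-up, event probabilities are 0.845 and 0.597, so 50 × (0.845 + 0.597) = 72.1 events. Schoenfeld power is Φ(√(72.1/4) × |ln 0.47| − 1.96) = 89% (Freedman 86.5%), not 80%. Nothing below depends on this.

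**Inputs from the documents.** 50 per arm: "Approximately 150 subjects will be randomized to the study, 50 subjects in each of the three treatment arms". Level: "Statistical significance will be established at the 0.025 level with one-sided hypothesis testing", stated for the primary endpoint and assumed here because SAP 7.3 sets none. Anchors: 87.2% GLS 0 or 1 at Day 30 (EVB-003); 26.5% and 8.3% with a 2-point composite response at Days 90 and 120 (EV-001).

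**Inputs assumed.** The full grade distributions, the share severe at Baseline, and a common odds ratio across grades.

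**Formula check, one stratum, N = 100.** Let p̄ be the average of the two arms' grade probabilities.

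- Ordinal information: V = (N/12)(1 − Σp̄³)
- Information from one cut: V = (N/4) p̄(1 − p̄)
- Power = Φ(ln OR × √V − 1.96)

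*Day 30-like*, 20U grades 0 to 3 = 0.45/0.42/0.11/0.02, OR 2.8. Average grades are 0.573/0.337/0.077/0.014.
- Ordinal: V = 8.333 × (1 − 0.227) = 6.44; Φ(1.030 × 2.538 − 1.96) = 74%.
- Cut 0/1: p̄ = 0.910, V = 25 × 0.910 × 0.090 = 2.05; Φ(1.030 × 1.433 − 1.96) = 31%.

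*Day 90-like*, 0.10/0.35/0.35/0.20, OR 2.7.
- Ordinal: V = 7.52, power 78%.
- Cut 0/1: p̄ = 0.569, V = 6.13, power 69%.

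The loss is about 9 points for a mid-scale cut and over 40 near the ceiling.

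**Simulation with the planned GLS definitions.** The assumed 20U grades were:

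| 20U grades | Severe at Baseline (0/1/2/3) | Moderate at Baseline (0/1/2) |
|---|---|---|
| Day 30 | .40/.42/.15/.03 | .65/.32/.03 |
| Day 90 | .08/.27/.45/.20 | .15/.55/.30 |
| Day 120 | .02/.10/.48/.40 | .05/.45/.50 |

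With 65% severe these give 87% GLS 0/1 at Day 30, and 28% and 10% 2-point responders at Days 90 and 120. Power at OR 2.5 (simulation standard error about 1 point):

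| Test | Day 30 | Day 90 | Day 120 |
|---|---|---|---|
| Ordinal, stratified by Baseline GLS | 60% | 67% | 65% |
| Best single cut, same stratification | 43% | 57% | 56% |
| 0/1, unadjusted | 22% | 54% | 40% |
| ≥1-point, unadjusted | 3% | 39% | 56% |
| ≥2-point, unadjusted | 37% | 56% | 33% |
| At least one of four unadjusted cuts (≥1, ≥2, ≥3-point, 0/1) | 56% | 75% | 70% |

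From unrounded values, the gains over the best stratified cut are 17, 11 and 9 points. Over OR 2 to 3 and 50 to 80% severe, the smallest gain was 4 to 5 points (Day 120, OR 2, 50% severe). With OR 1, the ordinal test rejects in about 2 to 3% of trials, and at least one of the four cuts in about 6 to 9%.

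**Sensitivity.** With a second set of assumed distributions (OR 2.8, 30% or 50% moderate), the gain over the best stratified cut was 9 to 17 points in seven of eight settings and 22 in the other, at Day 30.

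**The case against.** A reader might infer that a real 40U effect on depth would usually be missed. The documents do not support that. SAP 7.3 plans all the cuts together with no multiplicity rule, and under the assumptions above at least one of four GLS cuts is significant in 56 to 75% of trials. That is close to the ordinal test at Day 30 and above it later. The price is a false-positive rate about three times as high, with no rule for which cut counts. So the case rests on having one controlled test, not on lost signals.

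Other objections carry weight:

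- Within each Baseline stratum, the planned GLS cuts together recover the whole grade distribution. The information is shown, though no test uses it as a whole.
- Part of the gap to the unadjusted cuts comes from stratification. Without it, the ordinal test at Day 120 falls to about 51%, below the unadjusted ≥1-point cut. The fair comparison is with stratified cuts, and the 4-to-17-point figure uses those.
- The EV-001 anchors required investigator and subject to agree. Items 3 and 4 use one rater, whose rate cannot be lower.
- Proportional odds drives the result. If the whole effect crosses the one cut tested, that cut wins, 73% against 36%. If it lies only between grades 0 and 1, the 0/1 cut has 3% against 17%.
- Cuts at 0/1 and 2 points were the sponsor's Phase III endpoints, and SAP 7.3 exists to screen such definitions. Removing their tests would defeat that purpose.

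The last objection settles the form of the remedy: add, do not replace.

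**Conclusion.** The point holds as a low-cost improvement to exploratory analyses. The absence of any full-scale test is plain from the text. For GLS, one Baseline-stratified ordinal test has about 4 to 17 points more power than the best single stratified cut. The gain is much larger over end-of-scale cuts, such as 60% against 22% for 0/1 at Day 30. Neither end of the range is a bound, since one Day 30 setting reached 22.

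These sizes assume 50 per arm, one-sided 0.025, a roughly common odds ratio of 2 to 3 and illustrative grade distributions. They ignore exit from the study, which Protocol 10.2.5 allows from Day 90 and which leaves fewer, selected subjects later under either analysis.

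It may be tempting to carry the same figures over to GAIS and SSS. The documents give no grade distribution or anchor for either scale, so that gain is not quantified. Nor does the point touch the primary or secondary endpoints, which concern duration. The documents call the study not powered for inference, which limits the stakes but not the value of a better exploratory test.

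**What to change.** In SAP 7.3 and Tables 14.3.3.3.1 to 14.3.3.5.1:

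1. Add one proportional-odds model of the full score per scale, rater and visit: GLS and GAIS by Investigator and by subject, and SSS. Include treatment and Baseline GLS (the same rater's Baseline for GLS). A rank test stratified by Baseline GLS is an alternative for the p-value.
2. Report the common odds ratio, 95% CI and p-value for each pair of arms, and name this the main between-arm reading for that scale. That makes 5 lead tests per visit and pair, where 13 now stand unranked.
3. Name Days 30, 60 and 90 as the main visits. Handle exited subjects at later visits as in the responder rates.
4. Keep all planned responder rates and odds ratios as supporting results. They would show an effect confined to one grade boundary, where the retained cut can be more powerful than the ordinal test.

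The cost is SAP wording and one added block per table shell, with no new data. To count as prespecified, the change must be dated before database lock.
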